11.3.1 Safety Analyses

11.3.1.1 Adverse Events

All safety endpoints will be summarized using descriptive statistics and will be based on the safety analysis dataset.

All AEs will be coded based on the Medical Dictionary for Regulatory Affairs (MedDRA; Version 15.0 or higher). An AE will be considered a treatment emergent adverse event (TEAE) if the onset is after the first dose of study drug to 28 days following the last dose of study drug or if the condition was present at baseline but worsened after the first dose.

All AEs for each patient will be listed, including intensity grading, relationship to study drug, action taken and outcome. Patient listings of deaths, SAEs, and AEs leading to treatment discontinuation will be provided. Patient narratives will be provided for deaths, SAEs and other significant AEs. Summary tables will be prepared to examine TEAE severity and relationship to study treatment.

AE summaries will be produced separately for each dose cohort and overall, and each disease cohort by dose and overall. All summaries will show, dose cohort and overall, the number and percentage of patients experiencing at least 1 TEAE of each preferred term, arranged by system organ class, and the number of occurrences of the event. Separate summaries will be produced by relationship to study drug, by severity, and for those events with an incidence rate of at least 2% in any group or overall.

SAEs will be summarized in a similar manner; overall, by relationship to study drug, and by severity.

In addition to the above, summaries of the number and percentage of patients discontinuing the study due to AEs and, due to death, will be presented.

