1.1. Project Design

(Protocol Amendment #6). This is a Phase 1/2a, dose-escalation study of FF-10502-01. A total of up to N=161 patients with advanced solid tumors will be included in this study. In Phase 1 dose escalation, a total of up to 9 cohorts each will receive FF-10502-01 intravenously (IV) in 500 mL normal saline over a 1-hour period at doses of 8, 12, 18, 27, 40, 60, 90, 135 or 200 mg/m² weekly (Day 1, 8, 15) for three weeks, repeated every 28 days (= 1 cycle) until progression of disease. Once 6 patients are treated at the MTD in Phase 1, an additional 4 cohorts will be enrolled. Cohort 10 will enroll any patient with an advanced solid tumor who is otherwise eligible for this study (up to 20). Cohort 11 will enroll cholangiocarcinoma patients (up to 50). Cohort 12 will enroll gallbladder carcinoma patients (up to 10). Cohort 13 will enroll urothelial carcinoma patients (up to 27). Eligible patients enrolled in Phase 1 at the MTD may count towards the Phase 2a accrual.

Patients who demonstrate clinical benefit will be allowed to continue therapy with FF-1052-01 until progression of disease, observation of unacceptable adverse events (AEs), intercurrent illness or changes in the patient's condition that prevents further study participation.

During Phase 1 of the study, a Safety Review Committee (SRC) consisting of the actively recruiting investigators, the Medical Monitor, and FPHU, will review data from each cohort on an ongoing basis. Intermediate dose levels may be added if DLT is observed and it is recommended to do so by the SRC. During Phase 2a of the study, the SRC will review patient data at least quarterly and make recommendations to FPHU regarding the conduct of the trial.

The accrual for the Phase 1 dose escalation phase is expected to be 12 – 18 months. Accrual for the Phase 2a expansion phase is expected to be approximately 21 months, with the last patient followed every 3 months until death or patient's refusal to participate. The total study duration is expected to be approximately 57 months. The anticipated Phase 2a accrual rate is 3 – 5 patients per month for Cohort 10 and 1 – 2 patients with cholangiocarcinoma, gallbladder carcinoma and urothelial carcinoma (Cohorts 11, 12 and 13).

Safety will be assessed through the monitoring of AEs, clinical laboratory parameters (hematology, coagulation parameters, serum chemistry, and urinalysis), vital sign measurements, electrocardiograms (ECGs) and physical examinations.

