1.2. Objectives

1.2.1. Primary Objective

To determine the safety profile, maximum tolerated dose (MTD), dose-limiting toxicities (DLT) and recommended Phase 2 dose (RP2D) in patients who receive FF-10502-01 for treatment of advanced solid tumors.

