1.3.2. Selection and Timing of Doses

Phase 1: A single-patient dose escalation schema will be followed until the observation of \geq Grade 2 toxicity. One patient per cohort will be dosed and followed for 28 days through Cycle 1 for DLT. If no \geq Grade 2 toxicity is seen, the next patient will be enrolled at the next dose level. Dose escalation will proceed in this manner until Grade 2 or greater toxicity is observed in at least one patient per cohort during the first 28 days. At that point, the current dose cohort will be expanded to 3 patients before proceeding in standard 3+3 manner. The dose escalation in subsequent cohorts will proceed in standard 3+3 manner. For all patient cohorts, if 1 of 3 patients per cohort experiences DLT, the cohort will be expanded to 6. If 2 or more of 6 patients per cohort experience DLT, all further dose escalation will stop. If the next lowest dose has only 3 patients, 3 more patients will be treated at that dose to verify it as the MTD. If that dose turns out to be too toxic, then this process will be repeated until the MTD is found through dose de-escalation. If 0 of 3 or ≤ 1 of 6 patients per cohort experience DLT by Day 28 following dosing of FF-10502-01, dose escalation will proceed to the next cohort. The highest dose level below the dose level eliciting DLT in ≥ 2 patients will be declared the MTD. A total of 6 patients will be treated at the MTD. The MTD will be declared the RP2D. No intra-patient dose escalation will be allowed from previous dose levels until at least one patient has completed Cycle 1 at the higher dose level, with no Grade 2 or greater toxicities observed.

Dose level adjustments for DLT will be made. Patients who experience DLT at the first dose level, 8 mg/m², will not be dose-reduced, and will be discontinued.

Phase 2a: Patients in Cohorts 1 to 12 will receive FF-10502-01 on a weekly schedule for 3 weeks (Days 1, 8, and 15), repeated every 28 days. The Phase 2a dose regimen is FF-10502-01 90 mg/m², administered on Days 1, 8, and 15 of a 28-day cycle. Patients in Cohort 13 (urothelial carcinoma) will receive FF-10502-01 on a weekly schedule for 2 weeks (Days 1 and 8), repeated every 21 days.

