2.1. Sample Size and Power

A total of up to N=161 patients with advanced solid tumors are planned in this study.

Phase 1: The sample size reflects requirements associated with a single patient dose escalation until \geq Grade 2 toxicity is observed, thereafter a 3+3 design. A total of 3 to 54 patients are planned (1 to 6 patients in each of 9 dose cohorts).

Phase 2a: The sample size reflects four additional cohorts: Cohort 10 (advanced solid tumors) will enroll up to 20 patients, Cohort 11 (cholangiocarcinoma) will enroll up to 50 patients, Cohort 12 (gallbladder carcinoma) will enroll up to 10 patients, and Cohort 13 (urothelial carcinoma) will enroll up to 27 patients for a total of up to 107 patients.

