3.4.2. Adverse Events

AEs reported from the date of the first dose of study drug to 28 days following the last dose of study drug will be presented. All AEs will be coded based on the Medical Dictionary for Regulatory Affairs (MedDRA; Version 17.0 or higher). An AE will be considered a treatment emergent adverse event (TEAE) if the onset is after the first dose of study drug or if the condition was present at baseline but worsened after the first dose.

All AEs for each patient will be listed, including intensity grading, relationship to study drug, action taken and outcome. Table summaries and patient listings of deaths, serious TEAEs, and TEAEs leading to treatment discontinuation will be provided.

TEAE summaries will be presented for patients in Phase 1 dose escalation phase and for patients in Phase 2a expansion phase by disease cohort. All TEAE summaries will show the number and percentage of patients experiencing at least 1 TEAE for each preferred term, arranged by system organ class, and the number of unique occurrences of the event. Separate summaries will be produced by relationship to study medication, and by severity, and for those events with an incidence of at least 2% in any group or overall. Patients with multiple events will be counted only once per SOC and preferred term. For each level of summarization, the event with the highest level of severity, or strongest drug relationship will be presented. TEAEs with Grade 3 or Grade 4 and drug-related TEAEs with Grade 3 or Grade 4 will be summarized. TEAEs leading to study drug interruption or discontinuation, Grade 3 and 4 TEAEs, Serious TEAEs will be summarized and also provided in a separate listing. In addition, a summary of TEAEs for the total occurrences of the events will be provided.

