4.1. Mock Tables

The following tables will be presented for patients in the Phase 1 dose escalation phase and by disease cohort at MTD for patients in the Phase 2a expansion phase.

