4.3. Mock Listings

The following listings will be presented in Phase 1 dose escalation phase and patients in Phase 2a expansion phase.

- Inclusion Criteria Not Met
- Exclusion Criteria Not Met
- Protocol Violations/Deviations/Exemptions
- Demographics
- End of Treatment
- End of Study
- Medical History
- Prior Cancer Therapy
- Radiation Therapy History
- Physical Examination
- Prior Medications
- Concomitant Medications
- Primary Diagnosis
- Study Drug Administration
- Pharmacokinetic (PK) Blood Sample Collection
- Pharmacodynamic (PD) Blood Sample Collection
- Screening Target Lesion Assessment (Non-Lymphoma Solid Tumor)
- Target Lesion Assessment (Non-Lymphoma Solid Tumor)
- Screening Non-Target Lesion Assessment (Non-Lymphoma Solid Tumor)
- Non-Target Lesion Assessment (Non-Lymphoma Solid Tumor)
- Tumor Biopsy Collection
- Disease Response Assessment (Non-Lymphoma Solid Tumor)
- Best Overall Disease Response Assessment
- Treatment Emergent Adverse Events (TEAEs)

- Serious Treatment Emergent Adverse Events
- Treatment Emergent Adverse Events Leading to Dose Adjustment, Temporary Interruption, or Permanent Discontinuation of Study Drug
- Treatment Emergent Adverse Events Leading to Permanent Discontinuation from Study
- Dose Limiting Toxicities
- Deaths
- Hematology
- Coagulation Parameters
- T Lymphocytes and B Lymphocytes
- Chemistry
- Urinalysis
- Vital Signs
- 12-lead Electrocardiogram
- Other Procedures
- Long Term Follow-up

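### The SAP drops the by-dose adverse event summaries that the protocol requires for Phase 1, and plans no table of DLTs by dose level

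*SAP*

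**What the plan says.** The primary objective in SAP 1.2.1 is a dose-finding one: "To determine the safety profile, maximum tolerated dose (MTD), dose-limiting toxicities (DLT) and recommended Phase 2 dose (RP2D"). Phase 1 escalates through "8, 12, 18, 27, 40, 60, 90, 135 or 200 mg/m² weekly" (SAP 1.1), and SAP 2.1 sizes it by dose cohort: "A total of 3 to 54 patients are planned (1 to 6 patients in each of 9 dose cohorts"). The MTD rule in SAP 1.3.2 also works level by level: "The highest dose level below the dose level eliciting DLT in" two or more patients is declared the MTD.

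On presentation, Protocol 11.3.1.1 says "AE summaries will be produced separately for each dose cohort and overall, and each disease cohort by dose and overall", and adds that SAEs are to be summarised in the same way.

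SAP 3.4.2 says "TEAE summaries will be presented for patients in Phase 1 dose escalation phase and for patients in Phase 2a expansion phase by disease cohort". SAP 3.4 uses the same layout for all safety endpoints. SAP 4.1 applies it to the whole table list: "The following tables will be presented for patients in the Phase 1 dose escalation phase and by disease cohort at MTD for patients" in Phase 2a. Only Phase 2a is divided, and only by disease.

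Among the outputs, DLTs occur once, as the listing "Dose Limiting Toxicities" in SAP 4.3.

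**The concern.** A dose-escalation phase is read by dose level. The reader wants to see toxicity at each level, how it rises, and how many patients had a DLT out of how many at risk. The protocol planned for that in its adverse event section. The SAP, which is the document the tables will be programmed from, gives a layout without it and offers no reason.

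If the tables follow the SAP literally, the study report would describe Phase 1 toxicity without a dose axis. The count on which the MTD rests would appear only in a patient listing. The report would then not show, in any summary, the evidence for the dose carried into Phase 2a.

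**Working it through.** **1. The plan's own Phase 1 size.** Inputs from SAP 2.1: nine dose cohorts, up to 6 patients each. 9 × 6 = 54, which reproduces the stated maximum. Adding Phase 2a, 20 + 50 + 10 + 27 = 107, and 54 + 107 = 161, the stated total. The stated minimum of 3 is below 9 × 1 = 9, so it can arise only if escalation stops before all nine levels open.

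**2. The dose range.** 200 / 8 = 25-fold (SAP 1.1).

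**3. The two layouts side by side.**

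| Item | Protocol 11.3.1.1 | SAP 3.4, 3.4.2, 4.1, 4.3 |
|---|---|---|
| Phase 1 adverse events | Each dose cohort, and overall | Phase 1 patients; no dose split stated |
| SAEs | Same manner as adverse events | Same layout as other SAP tables |
| DLTs | Not addressed in this section | Listing only |

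SAP 4.1.6.2 names eight adverse event tables. None is described as by dose, and none covers DLTs. SAP Section 3 contains no DLT analysis. SAP 2.2 defines no DLT-evaluable set, so a DLT rate has no specified denominator.

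**4. What a display without dose columns would do (assumed counts).** Suppose two patients at one level have a DLT, the pattern that stops escalation, and no DLT occurs elsewhere. Exact (Clopper-Pearson) 90% intervals:

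- By dose level: 2/6 = 33.3% (6.3% to 72.9%).
- All of Phase 1 at the maximum size: 2/54 = 3.7% (0.7% to 11.2%).
- All of Phase 1 if only 20 patients were treated: 2/20 = 10.0% (1.8% to 28.3%).

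The size of the dilution depends on Phase 1 enrolment, which the documents cap but do not report. Single-patient cohorts at low doses make a number below 54 likely.

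**5. The 2% table.** SAP 3.4.2 restricts one TEAE table to events with at least 2% incidence. A single event is 1/6 = 16.7% in a full dose cohort. In an undivided Phase 1 column it is 1/50 = 2.0%, which qualifies, but 1/51 = 1.96% or 1/54 = 1.85%, which does not. This edge case needs Phase 1 to reach 51 or more patients. The event would still appear in the full table by preferred term.

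**6. An optional pooled column at one schedule.** Cohorts 10 to 12 share 90 mg/m² on Days 1, 8 and 15 (Protocol 8.2). Their caps sum to 20 + 50 + 10 = 80, or about 20 + 25 + 10 = 55 if Cohort 11 stops at its interim look. The chance of seeing at least one case of an event with an assumed true rate of 3% is 1 − 0.97^n:

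| n | 10 | 20 | 50 | 55 | 80 |
|---|---|---|---|---|---|
| Chance | 26% | 46% | 78% | 81% | 91% |

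Neither document promises this column.

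**The case against.** Several points on the other side are sound and limit the claim.

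- **Pooling is never stated.** A reader might infer that the SAP combines all dose levels into one column. That is the natural reading, but the SAP names the patients covered and gives table titles without column layouts. SAP 3.4.1 adds up exposure by dose cohort, and the 2% threshold applies to any group as well as overall. Both leave room for dose columns. What stands is that no dose split is specified where the protocol requires one.
- **The safety profile is tabulated.** A reader might conclude that no planned table serves the primary objective. That goes too far. SAP 4.1.6.2 and 4.1.6.3 plan TEAE tables by preferred term, relationship and severity, Grade 3 and 4 and serious TEAE tables, and laboratory shift tables. The gap is confined to the MTD, DLT and RP2D parts.
- **The dose decision does not depend on these tables.** The MTD comes from the 3+3 rule, with the Safety Review Committee reviewing each cohort as it accrues. Protocol 6.3 describes Phase 1 accrual in the past tense, and Protocol 8.5 already calls 90 mg/m² the RP2D. A report layout cannot alter that decision, so the documents do not support a claim that the MTD is unsafe or wrongly chosen.
- **Counts can be recovered by hand.** The patient number carries a cohort number that stays fixed when the dose changes (SAP 1.4.1), so a DLT listing showing it identifies the starting dose. Other listings cover the safety population and give the number treated. The number evaluable for DLT is still undefined, and a hand count is not a planned summary.
- **The protocol's requirement is limited.** Section 11.3.1.1 covers AEs and SAEs. It does not ask for exposure tables by dose, and Protocol 11.3.1.2 states no dose split for laboratory data.

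**Conclusion.** The point holds as a mismatch between SAP and protocol, with one further gap. The SAP omits the by-dose AE and SAE summaries required by Protocol 11.3.1.1, and it plans no table of DLTs by dose level. No SAP table as specified therefore reports toxicity along the 25-fold dose range, and the dose-finding parts of the primary objective have no planned summary.

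This should be fixed, but it is not critical. No decision rule or data collection is affected, the protocol already states the right adverse event layout, and the information can be rebuilt from listings. The dilution from 33% to between 3.7% and 10% is an illustration. It rests on assumed DLT counts, on assumed Phase 1 sizes of 54 and 20, and on the reading that Phase 1 is shown without dose columns. The textual mismatch needs none of these assumptions. SAP 2.4.5 and the content of the mock tables were not in the text available, so the conclusion rests on the sections cited.

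**What to change.** 1. In SAP 3.4.2 and 4.1, state that the Phase 1 TEAE, related TEAE, Grade 3 and 4, and serious TEAE tables have one column per dose level plus an overall column, matching Protocol 11.3.1.1. Group patients by assigned starting cohort, and allow for any intermediate level that the Safety Review Committee adds.
2. Add one table of DLTs by dose level: number with a DLT, number DLT-evaluable, number treated, and the DLT term. Define the DLT-evaluable set in SAP 2.2, consistent with the protocol's 28-day DLT follow-up.
3. Optional, and not required by the protocol: exposure and laboratory tables by dose level, and one pooled column for all patients started at 90 mg/m² on Days 1, 8 and 15 (Phase 1 at 90 mg/m² plus Cohorts 10 to 12). Each patient should be counted once, because Protocol 6.1 says eligible Phase 1 patients at the MTD may count towards Phase 2a while SAP 1.3.1 says they will. Cohort 13 stays separate because its schedule differs.

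The cost is SAP wording, extra columns and one short table. No new data are needed, since the cohort number is already in the patient number and DLTs are already to be listed.

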Statistical methods: Safety Endpoint Analyses: 
Safety endpoints for AEs include the following: incidences of all treatment-emergent adverse events (TEAEs) and all serious adverse events (SAEs); number and incidence of TEAEs and SAEs by severity; number and incidence of TEAEs and SAEs by relationship to study drug; number and incidence of all Grade 3 and 4 TEAEs and by severity and relationship to study drug; and discontinuation of patients from the study due to AEs or death. Safety endpoints for AEs, clinical laboratory tests, vital signs, ECG, and physical examination findings will be specified in the statistical analysis plan. Physical examination findings and ECGs will be listed. All other safety data will be summarized using descriptive statistics.
 Efficacy Endpoint Analyses: 
Response rates will be summarized using number and percentage of patients with a best response of CR, PR, SD or PD assessed by RECIST v 1.1 across all time points. For duration of response, duration of stable disease, PFS and OS, the Kaplan-Meier product-limit method will be used to estimate the median survival. Patients who do not have disease progression will be censored at the time of last contact.
 
Progression-free survival will be calculated from the date of first treatment to the date of progression or death.
 
Overall survival will be calculated from the date of first treatment to the date of death from any cause; patients who do not experience death will be censored at the time of last contact.
 
SAS Version 9.4 or higher for Windows (SAS Institute, Cary, NC) or higher will be used for all analyses.
 Pharmacokinetic and Pharmacodynamic Endpoint Analyses: Analysis plans will be described in the written plans provided by the laboratories performing the analyses.	

CONTENTS

2	SYNOPSIS	3
3	LIST OF ABBREVIATIONS.....	14
4	INTRODUCTION	17
4.1	FF-10502-01 Background	17
	Figure 1. Chemical Structure of FF-10502-01	18
4.2	ZK 820973 Preclinical Summary	18
4.2.1	ZK 820973 Preclinical Pharmacokinetics, Distribution, Metabolism, Excretion	18
4.2.2	ZK 820973 Preclinical Safety Pharmacology.....	19
4.2.3	ZK 820973 Genetic Toxicology	19
4.3	FF-10502-01 Preclinical Studies	19
4.3.1	FF-10502-01 In Vitro Anti-tumor Activity	19
	Table 1. Growth Inhibition of FF-10502-01 and Gemcitabine in Human Tumor Cell Lines ..	20
4.3.2	FF-10502-01 In Vivo Anti-tumor Activity.....	20

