10.1.5 Recording of Adverse Events

Each AE should be recorded in standard medical terminology on the AE CRF module. Whenever possible, the AE should be evaluated and reported as a diagnosis rather than as individual signs or symptoms. For example, cough, runny nose, sneezing, sore throat, and head congestion should be reported as 'upper respiratory infection'. If a definitive diagnosis is not possible, the individual signs and symptoms should be recorded. Dates of start (onset) and stop (recovery), action taken, and outcome will be recorded in the AE CRF module.

All clinically significant abnormal changes in laboratory parameters will be recorded as an AE on the AE module, with the following exceptions: clinically significant abnormal laboratory changes determined to be related to the study condition and concomitant conditions, eg, diabetes, of which the investigator was previously aware and that have not worsened.

The investigator will evaluate all AEs with regard to maximum intensity and relationship to study drug, as follows.

10.1.5.1 *Maximum Intensity*

Maximum intensity should be assigned using one of the severity grades as outlined in the National Cancer Institute Common Terminology Criteria for Adverse Events (NCI CTCAE v4.03); if the AE is not specifically listed in CTCAE v4.03, use the following grades:

- Grade 1: mild
- Grade 2: moderate
- Grade 3: severe
- Grade 4: life-threatening
- Grade 5: death

10.1.5.2 *Relationship to Study Drug*

The degree of certainty with which an AE is attributed to study drug (or alternative causes, eg, natural history of the underlying diseases, concomitant therapy, etc) will be determined by how well the event can be understood in terms of known pharmacology of the study drug and/or

reactions of similar nature previously observed with study drug. Each AE will be assigned one of the following five categories:

- Not related: There is not a temporal relationship to the study drug (eg, too early, too late), or there is a reasonable causal relationship to another drug, concurrent illness, or circumstance.
- Unlikely related: There is a temporal relationship to study drug, but there is not a reasonable causal relationship between the time of study drug administration and the AE (ie, it is doubtful the AE is related to the study drug); could be reasonably explained by other factors, including underlying disease, complications, concomitant drugs, or concurrent treatment.

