4.1.6.2. Adverse Event Summaries

- Summary of Treatment Emergent Adverse Events
- Treatment Emergent Adverse Events by System Organ Class and Preferred Term
- Treatment Emergent Adverse Events by Relationship to Study Drug
- Treatment Emergent Adverse Events by Severity
- Grade 3 and 4 Treatment Emergent Adverse Events
- Drug-related Grade 3 and Grade 4 Treatment Emergent Adverse Events
- Treatment Emergent Adverse Events with at least 2% Incidence in Any Group or Overall
- Serious Treatment Emergent Adverse Events

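### The planned high-grade and drug-related high-grade adverse event summaries stop at Grade 4, so fatal (Grade 5) events fall outside them and no listed SAP table gives drug-related events of Grade 3 or higher with deaths included.

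*SAP*

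**What the plan says.** The high-grade summaries are defined in SAP 3.4.2: "TEAEs with Grade 3 or Grade 4 and drug-related TEAEs with Grade 3 or Grade 4 will be summarized". The same section repeats the Grade 3 and 4 limit when it promises a separate listing. SAP 4.1.6.2 names the two resulting tables; the second is "Drug-related Grade 3 and Grade 4 Treatment Emergent Adverse Events". The SAP did not introduce the limit. The statistical methods part of the protocol synopsis gives the safety endpoint as "number and incidence of all Grade 3 and 4 TEAEs and by severity and relationship to study drug".

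On grading, Protocol 10.1.5 says "The investigator will evaluate all AEs with regard to maximum intensity and relationship to study drug, as follows". Section 10.1.5.1 refers to CTCAE v4.03 and, for terms not listed there, spells out five grades, the last being death. On counting, SAP 3.4.2 says "For each level of summarization, the event with the highest level of severity, or strongest drug relationship will be presented".

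Fatal events also appear elsewhere. SAP 4.1.6.2 lists "Treatment Emergent Adverse Events by Severity", with no grade restriction, and a table of serious events. SAP 3.4.2 adds "Table summaries and patient listings of deaths, serious TEAEs, and TEAEs leading to treatment discontinuation will be provided". SAP 3.4.6 summarises discontinuation due to death, and SAP 4.3 has a deaths listing. Protocol 11.3.1.1 adds "SAEs will be summarized in a similar manner; overall, by relationship to study drug, and by severity" and narratives for deaths.

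**The concern.** A table of severe toxicity should not look better because a toxicity killed the patient. Each event carries one maximum grade, so an event that ends in death is a Grade 5 event and does not meet a Grade 3 or 4 criterion. Read as written, the tables omit it. Any resulting error runs in one direction: the tabulated rate of severe toxicity can only be too low.

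The safety profile is part of the primary objective, and the Phase 2a cohorts are small enough for one patient to move a percentage visibly. The drug-related table matters most. It is the only table named in the SAP that crosses high grade with relationship to study drug, and it leaves out the drug-related events with the worst outcome.

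**Working it through.** The plan states no figure to reproduce. The check is a reading of the rules, followed by simple arithmetic.

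**Step 1. Do fatal events enter the adverse event data?** Yes. Protocol 10.1.6 has the cause of death recorded as the serious event, and serious events are also entered on the adverse event form. There is one limit: under Protocol 10.1.1, significant worsening of the disease under study is not recorded as an adverse event, so many disease-related deaths will not be there.

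**Step 2. What grade do they carry?** Grade 5, under maximum-intensity grading. The protocol writes out the five-grade scale only for terms not in CTCAE. I assume that CTCAE-listed terms with a fatal outcome are also Grade 5.

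**Step 3. Do they meet the table criterion?** No. Grade 5 is neither Grade 3 nor Grade 4, and nothing in either document adds it.

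**Step 4. When does the patient, and not just the event, disappear?** The SAP does not say whether records are filtered to Grades 3 and 4 before or after the worst event is taken. Table shells are not shown, so an overall any-event row is assumed.

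| Patient's high-grade events | Filter first, then worst | Worst first, then filter |
|---|---|---|
| One term, Grade 5 only | Absent from the table | Absent from the table |
| Term X Grade 5, term Y Grade 3 | In row Y and the any-event row; not in row X | In row Y; not in row X or the any-event row |
| Term X recorded twice, Grade 3 and Grade 5 | In row X at Grade 3 and in the any-event row | Absent from the table |

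Loss from the any-event rate is certain only in the first case, a patient with no other Grade 3 or 4 event. In the drug-related table the same condition applies to drug-related events: the patient is certain to be lost only if the fatal event is drug-related and there is no other drug-related Grade 3 or 4 event.

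**Step 5. Size per such patient.** The patient stays in the safety population, so the shortfall is 1/n. With the maximum cohort sizes from SAP 2.1:

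- Cohort 11: 1/50 = 2.0 points
- Cohort 13: 1/27 = 3.7 points
- Cohort 10: 1/20 = 5.0 points
- Cohort 12: 1/10 = 10 points
- A six-patient dose cohort, where results are shown by dose as Protocol 11.3.1.1 plans: 1/6 = 16.7 points

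With k such patients the shortfall is k/n. It is larger if a cohort enrols fewer than its maximum. The documents give no expected number of fatal events, so k cannot be estimated from them.

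**Step 6. Can the missing figure be read from another listed table?** For all events of a given term, yes: the by-severity table has no grade limit. For drug-related events, no. SAP 4.1.6.2 lists severity and relationship as separate tables, and one serious-event table with no stated split. The protocol's serious-event summaries are by relationship and by severity, but the protocol does not say that the two are crossed.

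**The case against.** The strongest reply is that nothing is lost from the report. A fatal event appears in the by-severity table, the serious-event table, the deaths outputs and the full adverse event listing, which shows grade, relationship and outcome. A death is by definition a serious event, so the protocol's serious-event summary by relationship would include drug-related deaths. Showing Grades 3 and 4 together with deaths reported separately is a recognisable reporting choice, and the SAP follows the protocol synopsis in making it. No decision turns on these tables: the dose-limiting toxicity definition already covers non-hematologic events of Grade 3 and above without an upper limit, and the maximum tolerated dose follows from those counts.

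Most of this stands. A reader might infer that deaths go unreported, or that a fatal case disappears from every severity summary; the outputs just named rule out both. A reader might also assume a rate of fatal events, say 5 to 10% of patients, and conclude that severe toxicity is understated by up to that much. The documents give no such rate, disease worsening is kept out of the adverse event data, and the figure would also require that none of those patients had another Grade 3 or 4 event.

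What does not fall is the drug-related table. No other listed SAP table supplies its missing fatal events at the same level of detail; they would have to be assembled from listings. The dose-limiting toxicity wording also shows that the documents use an open-ended Grade 3 threshold elsewhere.

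**Conclusion.** The point holds as an under-count in two tables and the matching listing, not as a failure to report deaths. As written, fatal events are outside the high-grade and drug-related high-grade summaries. A patient with no other Grade 3 or 4 event is missing from the numerator, at a cost of 2.0 to 10 points per patient across the Phase 2a cohorts at their maximum sizes. For other patients the effect depends on an order of operations that the SAP leaves open. The substantive gap is that no listed SAP table gives drug-related events of Grade 3 or higher with fatal ones included.

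This rests on a literal reading of the table definitions and on fatal events being coded Grade 5. It does not affect dose-limiting toxicity counts, the maximum tolerated dose or any hypothesis. I rate it a cheap improvement.

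**What to change.** - In SAP 3.4.2 (summaries and listing) and the two table titles in SAP 4.1.6.2, replace the Grade 3 and 4 wording with *Grade 3 or higher (including Grade 5)*.
- Show Grades 3, 4 and 5 in separate columns, so that the Grade 3–4 figures remain available.
- State that each patient's worst grade is taken before the Grade 3 or higher cut is applied and, in the drug-related table, that it is the worst grade among that patient's drug-related events.
- Make the same change in the statistical methods part of the protocol synopsis, or record the difference in the SAP as a documented departure.

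The cost is table wording, one extra column and a small programming specification. The only downside is the matching protocol wording or the note of departure. No new data are needed.
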